### **Secondary Outcomes**

For secondary outcomes, GLMs will include treatment as a within-subjects factor and a repeated measures factor for variables with multiple observations. Cognitive behavioral performance will comprise six test measures of cognitive control (Maze, Digit Span, Verbal Interference Color and Word, Switching of Attention, and GoNoGo), and quality of life, four domains (physical health, psychological health, social relationships, and environment) as measured by the World Health Organization Quality of Life – Brief (WHOQOL-BREF) Scale. Planned paired t-test contrasts will test for the effect of GIR on change in each set of individual secondary measures in each general linear model. The secondary measures of depression symptom severity (measured by the 17-item Hamilton Depression Rating Scale and Quick Inventory of Depressive Symptoms-Self Report), global satisfaction with life (assessed using the Satisfaction With Life Scale), and suicidality (measured by the Columbia-Suicide Severity Rating Scale Ideation Score) are exceptions that do not have repeated measures.

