##### **4. Monitoring During the Study:**

Participants will be monitored regularly for treatment side effects and any health status changes that might put them at risk. Participants will be monitored every week for side effects generally and also specifically (i.e., with quantitative scales) for mood changes and suicidality. All significant changes described by participants and/or measured in the scales will be recorded in the patients' case report forms, immediately reported to prescribing psychiatrists (in case data were collected by other research personnel), and all necessary actions will be taken for participants' safety and well-being. Participants will be reminded and reassessed for the following:

- Use of birth control (females of childbearing potential),
- Alcohol and drug abstinence, and
- Changes to current medications.

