**g. Study Endpoint(s)**

The endpoint for primary and secondary measures will be 8 weeks after initiation of GIR or placebo, regardless of the study outcomes. Additional measures will be collected at the final endpoint of 10 weeks. If a subject reports a significant adverse event or worsening depression, the participant will be removed from the study. The study will not be terminated prematurely in the event that participants randomized to GIR have greater improvement than participants randomized to placebo.

---

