**h. Eligibility Criteria**

**i. Inclusion Criteria**

- 18-69 years of age (inclusive)

- Go-NoGo fMRI task-evoked dLPFC  $\leq$  - 0.5 SD below the mean of normative sample
- Behavioral cognitive control performance  $\leq$  - 0.5 SD below the mean of normative sample on a Maze, Digit Span, and/or Verbal Interference (Stroop) task administered using WebNeuro
- Score  $\geq$  14 on the 17-item Hamilton Depression Rating Scale-17 (HDRS-17)
- Meets DSM-5 diagnostic criteria for current, past, or recurrent nonpsychotic major depressive disorder established by MINI Plus
- Medication naïve to guanfacine
- Fluent and literate in English, and show non-impaired intellectual abilities to ensure adequate comprehension of the task instructions
- Written, informed consent
- fMRI scanning eligibility, including no evidence of any form of metal embedded in the body (e.g., metal wires, nuts, bolts, screws, plates, sutures), as these produce artifacts when brain imaging. All potential subjects will need to successfully complete the screening forms at the Stanford Center for Cognitive and Neurobiological Imaging (CNI).

ii. Exclusion Criteria

- Presence of suicidal ideations representing imminent risk, defined by a score of  $>$  8 on the MINI-Plus, or by clinician judgement
- Lifetime history of medical illness or injury that may compromise cognitive functioning or interfere with assessments as deemed by the study physician (such as neurological disorders such as seizures or stroke, Parkinson's disease, dementia, or traumatic brain injury)
- Severe impediment to vision, hearing, and/or hand movement likely to interfere with ability to complete the assessments, or are unable and/or unlikely to follow the study protocols
- Pregnant, breastfeeding or unwilling or unable to use adequate birth control throughout the study
- Loss of consciousness for  $>$  10 minutes during lifetime
- Any contraindication to being scanned in the 3.0T scanner at the CNI such as having a pacemaker or implanted device that has not been cleared for scanning at 3.0 Tesla
- Previous or current DSM-5 bipolar disorder (I, II, not otherwise specified) or psychosis
- Meets criteria for DSM-5 alcohol or substance use disorder within the last 12 months
- Meets criteria for current DSM-5 PTSD, OCD, or eating disorder
- Concurrent participation in other intervention or treatment studies

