These reports will be filed with the PI, who will file them with the Human Participants IRBs. The annual reports will also be filed with the IRB. The reports will enumerate the dates that the committee met and its procedures for monitoring participants' safety and confidentiality and data integrity. There will be regular, ongoing communication between the PI and the IRB. IRB protocols and informed consent documents will be annually reviewed by the IRB. The PI will take responsibility for reporting any serious adverse event (SAE) to the IRB within 24 hours according to standard regulations. A SAE is defined as follows: death, life-threatening adverse event, inpatient hospitalization, persistent or significant disability/incapacity, and medically significant event.

- i. Person(s) responsible for Data and Safety Monitoring  
The PI.
- ii. Frequency of DSMB meetings  
NA
- iii. Specific triggers or stopping rules  
See study endpoints.
- iv. DSMB Reporting  
A summary of the report will be submitted to the IRB for review.
- v. Will the Protocol Director be the only monitoring entity? (Y/N)  
Yes
- vi. Will a board, committee, or safety monitor be responsible for study monitoring? (Y/N)  
N

---

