## Statistical Analysis Plan

### **Primary Outcome**

We will evaluate the primary cognitive control circuit measure by testing the effect of 8 weeks of guanfacine immediate release (GIR) using a general linear model (GLM). This model will include a within-subjects factor for treatment (pre- vs. post-treatment sessions) and a within-subjects repeated measures factor for cognitive control circuit function, comprising five measures: task-evoked activation of the dorsal anterior cingulate cortex (dACC), left dorsolateral prefrontal cortex (dLPFC), right dLPFC, and connectivity between these regions. The analysis will assess the main effect of treatment and, secondarily, the interaction between treatment and circuit measure. Planned paired t-tests will evaluate the effect of GIR on changes in individual circuit measures.

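### The only planned suicidality analysis is a mean baseline-to-week-8 change in C-SSRS ideation on complete pairs, which can hide individual worsening; add a descriptive per-participant count

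*SAP*

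**What the plan says.** **Analysis.** For secondary outcomes the SAP (Secondary Outcomes) states that "GLMs will include treatment as a within-subjects factor and a repeated measures factor for variables with multiple observations". It then names depression severity, life satisfaction and "suicidality (measured by the Columbia-Suicide Severity Rating Scale Ideation Score) are exceptions that do not have repeated measures". The SAP's Primary Outcome section gives the meaning of the treatment factor: a "within-subjects factor for treatment (pre- vs. post-treatment sessions"). The protocol fixes the time (section 2.g): "The endpoint for primary and secondary measures will be 8 weeks after initiation of GIR or placebo". The SAP's final section handles missing data by listwise deletion and reports Cohen's d with a 95% CI.

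**Data collected.** The protocol (section 2.b.4) says: "Participants will be monitored every week for side effects generally and also specifically (i.e., with quantitative scales) for mood changes and suicidality". Section 2.a lists suicidality among the items assessed at visits and virtual monitoring, with contacts in each of weeks 1 to 10.

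**Individual handling.** Section 2.b.4 also says: "All significant changes described by participants and/or measured in the scales will be recorded in the patients' case report forms", with immediate report to the prescribing psychiatrist. Section 9.c requires a risk assessment when ideation is expressed. Section 9.e requires reports to the IRB on serious and unexpected events.

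**Removal.** Section 2.g takes a participant out of the study on a report of a significant adverse event or of deterioration in depression. Under section 9.d, follow-up after early termination takes place only if there is an adverse event.

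Neither document plans a count of participants with new or worse ideation, a worst-value summary, a shift table, or any group-level use of the suicidality assessments between baseline and week 8.

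**The concern.** A mean change answers whether ideation moved on average. For a depressed group off psychotropic medication and starting a study drug, a reader will also want to know how many people had new or worse ideation. The planned summary can miss that in three ways.

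1. **Netting.** One participant's rise is offset by another's fall. Entry excludes "Presence of suicidal ideations representing imminent risk" (protocol section 8.h.ii) and sets no minimum level of ideation, so some participants may start at zero, where the score can only rise, while others have room to fall.
2. **Timing.** A rise that appears after baseline and has settled by week 8 contributes nothing.
3. **Deletion.** A participant removed under section 2.g may have no week-8 score and is then excluded listwise. The people of most interest can leave the calculation, and the remaining mean moves towards improvement.

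At stake is a trial report that says ideation was unchanged or improved, with no accompanying figure for how many participants worsened.

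**Working it through.** The documents give no expected rate, baseline distribution or power figure for suicidality, so there is no stated figure to reproduce. The check asks what the planned analysis would show in cases where the number who worsened is known.

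**Inputs.** Planned enrollment 25 (protocol section 8.a); two-sided 0.05 and listwise deletion (SAP, final section); week-8 endpoint (protocol section 2.g). Assumed: 8 participants fall by 1 point, 3 rise by 2 points, 14 are unchanged.

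**Formulas.** For a single score with a two-level within-subjects factor, the model reduces to a paired t-test on the change d. Mean = Σd/n; SD² = (Σd² − n·mean²)/(n − 1); t = mean/(SD/√n).

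**Case 1: all 25 have a week-8 score and the rises persist.**
- Σd = 8(−1) + 3(2) = −2, so mean = −2/25 = −0.08
- Σd² = 8 + 12 = 20, so SD = √((20 − 0.16)/24) = 0.909
- t = −0.08/0.182 = −0.44 on 24 df, p = 0.66, 95% CI −0.46 to 0.30

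**Case 2: the same three rises resolve before week 8.**
- Mean = −8/25 = −0.32; SD = √((8 − 2.56)/24) = 0.476
- t = −3.36 on 24 df, p = 0.003, 95% CI −0.52 to −0.12

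**Case 3: the three who worsened are removed without a week-8 score.**
- n = 22; mean = −8/22 = −0.36; SD = √((8 − 64/22)/21) = 0.492
- t = −3.46 on 21 df, p = 0.002, 95% CI −0.58 to −0.15, d = −0.74

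In all three cases 3 of 25 participants (12%) had worse ideation at some point. The planned result is no change in the first case and nominally significant improvement in the other two.

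**What a count would show** (exact Clopper-Pearson 95% CI, n = 25):

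| Participants with new or worse ideation | Percent | 95% CI |
|---|---|---|
| 0 | 0% | 0 to 13.7% |
| 1 | 4% | 0.1 to 20.4% |
| 3 | 12% | 2.5 to 31.2% |
| 5 | 20% | 6.8 to 40.7% |

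**How much such a count drifts upward by chance.** Suppose each of 8 weekly assessments independently had probability q of a chance rise over baseline. The expected share with any increase is 1 − (1 − q)⁸: 7.7% at q = 1%, 14.9% at 2%, 33.7% at 5% and 57.0% at 10%. The values of q and the independence are assumptions. They show why the count must be presented as descriptive.

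**The case against.** The strongest reply is that suicidality is monitored closely regardless of the SAP. Weekly scales, case report forms, immediate report to the prescribing psychiatrist, a risk assessment when ideation is expressed, and reporting of serious events to the IRB within 24 hours are all in the protocol. This stands. Section 9.e asks "Will the Protocol Director be the only monitoring entity" and answers yes, with no board. A reader might infer that the final analysis is therefore the only structured readout of this risk, or that worsening would go unnoticed. The documents do not support either inference. What remains is narrower: the planned report to the IRB is built around serious and unexpected events, so new non-serious ideation need not appear in any group-level summary.

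A second reply concerns the phrase about repeated measures. A reader might take it to mean that ideation is scored too few times. In context it separates single scores from outcomes with several components, such as the six cognitive tests or four quality-of-life domains; it does not describe time points. The pre/post reading rests on the treatment factor and the week-8 endpoint, and it is unaffected.

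Third, the sizes depend on an assumed split. That is correct. The documents give no baseline C-SSRS distribution, and the sample must score at least 14 on the HDRS-17, so it cannot be claimed that most participants start at the floor. Netting and deletion can happen; nothing shows that they will.

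Fourth, a worst-of-many-visits count against a single baseline is biased upward, and the SAP model has no comparator term, although the protocol mentions placebo. This also stands. It argues against replacing the planned outcome with the count, though not against showing the count beside it.

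**Conclusion.** The point holds as a gap in aggregate analysis and reporting. The planned mean change is a legitimate answer to a question about average symptom effect, but it cannot show how many participants had new or worse ideation. It ignores assessments between baseline and week 8, and together with removal and listwise deletion it can turn worsening into apparent benefit. In the illustration, the same 12% who worsened go with a mean of −0.08 (p = 0.66), −0.32 (p = 0.003) or −0.36 (p = 0.002), depending only on whether the rises persist, resolve or lead to removal.

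These figures rest on an assumed split and, in the third case, on removed participants having no week-8 score. The protocol does not say whether one would be obtained. The removal rule concerns depression and adverse events and not ideation as such, so the overlap with worse ideation is plausible but not stated. Weekly use of the C-SSRS is not established either: section 2.b.4 refers to quantitative scales without naming them.

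**What to change.** Keep the planned mean change. Add to the SAP's Secondary Outcomes section a descriptive safety table:

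- **Who:** every participant who took at least one dose, including those who left early, with data up to the day of removal.
- **What:** the number and percent with new ideation (baseline score 0; also give the number with baseline 0 as denominator) and with any increase over their own baseline, at any post-baseline assessment through week 8.
- **Precision:** exact 95% CIs.
- **Weeks 9 and 10:** shown separately, because participants are then tapering, cross-titrating or continuing.
- **Caveat in the table note:** a worst value over many visits rises by chance and, without a comparator in the model, is not an estimate of drug effect.

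In protocol section 2.b.4, name the scale used for the weekly suicidality assessment so that it matches the baseline scale.

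The cost is one SAP paragraph and one table if the C-SSRS ideation items are already used weekly. If another scale is in use, data collection changes slightly. No treatment or clinical rule changes.

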### **Significance, Multiple Test Correction, and Handling Missing Data**

A two-sided significance level of 0.05 will be applied to each analysis within each modality for both primary and secondary outcomes. Corrections for multiple testing across modalities will not be applied, as each outcome targets a distinct hypothesis about the effect of GIR on cognitive, behavioral, symptom, and functional measures. Effect sizes (Cohen's d) will be reported for each outcome, along with 95% confidence intervals, to aid interpretation of clinical meaningfulness. Missing data will be handled using listwise deletion.

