**a. Procedures**

1. Recruitment and screening: Participants experiencing depressive symptoms and not taking any psychiatric medications as determined by a 5 half-life wash out period will be recruited from the community, including students and employees at Stanford. Recruitment will come primarily from Facebook ads, which will use only IRB approved material. A flyer will also be physically posted on boards in public locations in order to include a variety of sources for the study.
2. Individuals will need to participate in 3 screening visits in order to enroll in the study. During the first visit, participants will review informed consent, be administered a clinical interview, and be sent instructions for completing cognitive testing at home.
3. If eligibility after this initial screening visit, the second visit will be a medical screen in order to ensure participants are safe to take GIR and will include standard blood tests, medical history, vitals, and a urine drug test.
4. If the participant meets medical and cognitive criteria, functional magnetic resonance imaging (fMRI) scans will be undertaken at another study visit at The Stanford Center for Cognitive and Neurobiological Imaging (CNI). Using a participant's task-evoked activity

in the dorsolateral prefrontal cortex (dLPFC) and performance on objective cognitive testing, we will apply thresholds using established healthy norms to select participants within the cognitive biotype+ group.

5. Participants will receive GIR for a period of 8 weeks sent to their place of residence from Mariner pharmacy.
6. Participants will be seen in-person or virtually by a study clinician at weeks 2, 4, 6, 8, and 10 and an appropriately trained clinical research coordinator at weeks 1, 3, 5, 7, and 9. All subjects will have an fMRI scan after 6-8 weeks of taking GIR. During in-person visits and virtual monitoring, we will assess participants for the following: changes to symptoms, function, and suicidality, adherence to GIR, changes to concomitant medication(s), adverse events (AEs), birth control usage compliance, likelihood of pregnancy (female participants of childbearing potential), and vital signs if appropriate.

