**Safety Measures Upon Termination:**

After a participant's completion of or early termination from the study, participants will be followed up only in the case of an adverse event. If an adverse event occurs, the participants will be followed by the study MD until the adverse event is resolved. Referrals will be given if needed.

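### Removal for worsening depression combined with listwise deletion would tilt the HDRS-17 and QIDS-SR change toward benefit, and no planned analysis would show it

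*SAP*

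**What the plan says.** **Removal.** Protocol section 2.g: "If a subject reports a significant adverse event or worsening depression, the participant will be removed from the study". Section 9.e, asked for specific triggers or stopping rules, answers "See study endpoints", so 2.g is the operative rule. It states no threshold for worsening.

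**Endpoint.** The same section says: "The endpoint for primary and secondary measures will be 8 weeks after initiation of GIR or placebo".

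**After removal.** Under the heading on safety measures upon termination (section 9.d), after completion or early termination "participants will be followed up only in the case of an adverse event". No exit or week-8 outcome assessment is described for a removed participant.

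**Analysis.** The SAP, under Secondary Outcomes, tests depression severity (HDRS-17 and QIDS-SR) with treatment, meaning pre versus post, as a within-subject factor. On missing values the SAP has one sentence: "Missing data will be handled using listwise deletion". It plans Cohen's d with 95% confidence intervals and a two-sided 0.05 level. It describes no imputation, mixed model or sensitivity analysis.

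**Interim data.** Protocol section 2.b.4: "Participants will be monitored every week for side effects generally and also specifically (i.e., with quantitative scales) for mood changes and suicidality". Section 2.a lists "changes to symptoms, function, and suicidality" among the things checked during monitoring, and section 8.k pays for phone visits with completed questionnaires. The scales are not named.

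**The concern.** The reason for removal and the outcome are the same construct. A participant removed for worsening before week 8 has no described post value, so listwise deletion drops that person entirely, including the baseline score and anything recorded before removal. What remains is the mean change among people who did not worsen enough to be removed.

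The SAP offers effect sizes and intervals as an aid to judging clinical meaningfulness. With such removals, both would describe that selected group, and a reader would have no planned analysis against which to see the difference.

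**Working it through.** The documents give no power calculation, SD of change, dropout rate or removal threshold, so there is no stated figure to reproduce. The direction can be derived. The size can only be illustrated.

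**Step 1: identity.** With n enrolled and k removed, let D be the amount by which the removed participants' mean week-8 change would have been worse than the completers'. Then

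shift toward benefit = (k/n) × D.

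n = 25 comes from Protocol section 8.a; k and D are assumptions.

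| k | D = 5 points | D = 10 | D = 15 |
|---|---|---|---|
| 1 | 1/25 × 5 = 0.2 | 0.4 | 0.6 |
| 2 | 0.4 | 0.8 | 1.2 |
| 3 | 0.6 | 1.2 | 1.8 |
| 5 | 1.0 | 2.0 | 3.0 |

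The shift is toward benefit when D is positive, zero when D = 0 or k = 0, and reversed if removed participants would have recovered more than completers.

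**Step 2: imperfect trigger.** Someone removed for worsening might have recovered by week 8, so let the removal trigger have correlation ρ with the week-8 change. Simulation: n = 25, no true change, the k highest triggers removed, paired t-test at two-sided 0.05, 100,000 trials per setting. Each cell gives the shift in SDs of change and the benefit-direction error (nominal 2.5%).

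| k | ρ = 0.5 | ρ = 0.7 |
|---|---|---|
| 1 | 0.04; 4.0% | 0.06; 5.0% |
| 2 | 0.08; 5.7% | 0.11; 8.2% |
| 3 | 0.11; 7.7% | 0.15; 12.1% |
| 5 | 0.17; 12.0% | 0.24; 21.4% |

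The shift is proportional to ρ, which gives a check: for k = 5 the value at ρ = 1 is 0.34 SD, and 0.5 × 0.34 = 0.17 and 0.7 × 0.34 = 0.24. At ρ = 0.2 the range is 0.02 to 0.07 SD and 3 to 5%; at ρ = 0 there is none; ρ = 1 (up to 0.34 SD and 46%) is an extreme bound. At an assumed SD of 5 to 7 HDRS-17 points, 0.04 to 0.24 SD is 0.04 × 5 = 0.2 to 0.24 × 7 = 1.7 points.

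**Step 3: average improvement.** Assumed random-walk course: true change SD 6 at week 8, error SD 1.5, removal at week 2, 4 or 6 on an observed rise of 6 points. Mean improvements of 0, 4 and 7 points give 4.9, 2.3 and 1.2 removals and biases of 1.7, 0.85 and 0.46 points. At a 4-point improvement the full-data test is already significant in 85% of trials, so the damage is then mainly to the estimate and Cohen's d.

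**Step 4: how far alternatives correct it.** Assume the same scale is given at weeks 0, 2, 4, 6 and 8, no true change, and removal at an observed rise of 6 points. Bias in points (negative is toward benefit) under two assumed courses with the same SD of change:

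| Analysis | Random walk | Exchangeable visit-to-visit variation |
|---|---|---|
| Completers | −1.65 | −1.85 |
| Mixed model, AR(1) | −0.34 | +0.56 |
| Mixed model, compound symmetry | −0.89 | −0.04 |
| Last value carried forward | +0.18 | +1.58 |

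The ranking of the two covariance structures reverses with the course, and carry-forward can err almost as far as deletion, in the other direction. If only a baseline value exists, a likelihood analysis leaves 65 to 87% of the bias at ρ = 0.5 to 0.7 (pre-post correlation 0.3 to 0.7). Assigning removed participants zero change is also weak: with no true change it keeps (25 − k)/25 of the shift, which is 24/25 = 96% for one removal and 20/25 = 80% for five.

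**The case against.** The strongest objection concerns size. The point is conditional on removals that may never happen, and every figure above rests on assumed inputs. One removal moves the estimate by only 0.04 to 0.06 SD at ρ = 0.5 to 0.7. The error rates assume no pre/post change, yet entry requires an HDRS-17 of at least 14 and the test is pre/post, so some mean improvement is likely even with an inactive drug. The outcomes are secondary. All of this stands, and it limits the size without changing the expected direction.

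A reader might infer more than the documents support in four places.

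- **Repeated measures.** The SAP says that depression severity, life satisfaction and suicidality "are exceptions that do not have repeated measures". This could be taken to contradict the interim monitoring in the Protocol. It most naturally does not: the SAP's repeated-measures factor is a set of parallel measures (five circuit measures, six cognitive tests, four quality-of-life domains), and these scales are exceptions because each yields one score.
- **Exit assessment.** Section 9.d could be read as ruling one out. It deals with safety follow-up. If worsening is recorded as an adverse event, it provides clinical follow-up until resolution, and the manual of procedures (section 2.b.5) is not available. The supported statement is that no such assessment is described.
- **Interim scores.** Weekly quantitative scales might be assumed to be HDRS-17 or QIDS-SR. Neither document says so.
- **Other outcomes.** The same bias might be assumed for the primary circuit and cognitive measures. Those participants would be deleted there too, but nothing in the documents fixes the direction. For suicidality the same direction is plausible but not established.

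**Conclusion.** The point holds in conditional form. If anyone is removed for worsening depression before week 8, the HDRS-17 and QIDS-SR change, with its Cohen's d and confidence interval, is a completer result selected on that outcome and expected to shift toward benefit. The SAP has nothing that would show it. The direction rests on one assumption: that people removed for worsening would on average have had a worse week-8 change than completers.

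Confidence is high in the mechanism and expected direction, and low in any particular size. The illustrated range (0.04 to 0.24 SD, 4 to 21% benefit-direction error) is small for a single removal, becomes material at about two or three of 25, and shrinks with average improvement. This should be fixed, but it does not undermine the primary analysis.

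**What to change.** 1. **Main analysis of HDRS-17 and QIDS-SR.** In the SAP, replace listwise deletion with a likelihood-based repeated-measures model on all available observations, including interim scores if the same scale was given. Name the scales and weeks. Prespecify the covariance structure, a fallback if it does not converge, and small-sample degrees of freedom. The documents support no particular structure. If only baseline is available, state that the correction is small.
2. **Sensitivity analysis.** Prespecify one that treats removal for worsening as unfavourable, preferably a tipping-point shift over a stated range. Carry-forward may be added but should not stand alone.
3. **Reporting.** Give the numbers removed for worsening and for adverse events, by arm if there is a placebo arm, since unequal removal could move a between-arm contrast either way. Section 9.e already has retention and attrition under review.
4. **Clarification.** State whether willing participants who are removed still complete the already scheduled week-8 outcome assessments, and if so whether values after treatment has stopped or changed count toward the estimand. No change to the clinical removal rule is proposed.

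The cost is mainly SAP text, plus a short clarification of Protocol sections 2.g and 9.d. Estimates may become less favourable.

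### In the six-test cognitive model, listwise deletion removes a participant for one missing test score and discards that person's intact pre/post pairs on the other tests

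*SAP*

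**What the plan says.** The SAP section on significance, multiple testing and missing data gives one rule: "Missing data will be handled using listwise deletion". It does not say whether the list is one model, one modality or the whole data set. It plans no available-data model, imputation, minimum number of tests, rule for a failed test, or sensitivity analysis.

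The models it applies to are as follows.
- SAP, Primary Outcome: a pre/post session factor is crossed with "a within-subjects repeated measures factor for cognitive control circuit function, comprising five measures", which gives 10 values per person.
- SAP, Secondary Outcomes, cognition: "Cognitive behavioral performance will comprise six test measures of cognitive control", which over two sessions gives 12 values per person.
- SAP, Secondary Outcomes, quality of life: four WHOQOL-BREF domains, which gives 8 values per person.
- SAP, Secondary Outcomes, depression severity, life satisfaction and suicidality: these "are exceptions that do not have repeated measures", so the problem does not arise for them.

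Paired t-tests on individual measures follow each model. For the secondary measures the SAP places them inside each general linear model, which suggests that they use the same reduced set of participants. The Protocol (section 8.a) plans to enrol 25.

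**The concern.** A repeated-measures GLM analysed listwise needs every cell filled. If one of a participant's 12 cognitive values is absent, the model drops the other 11, including five complete pre/post pairs. Those pairs carry direct information on change, and nothing is wrong with them.

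Cognitive tests are separate tasks, so one can be skipped, interrupted or invalid while the rest are sound. With 25 participants and no stated margin for attrition, each avoidable exclusion costs noticeable precision. What is at stake is the power and interval width of the secondary cognitive result. The retained group may also differ from the enrolled one if people who fail a test change differently from those who do not.

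**Working it through.** **Inputs from the documents.** N = 25 (Protocol 8.a); 6 tests × 2 sessions = 12 cognitive values, 5 × 2 = 10 circuit values, 4 × 2 = 8 quality-of-life values (SAP, Primary and Secondary Outcomes); two-sided alpha 0.05 (SAP). The documents state no power calculation, effect size, dropout rate or missing rate, so there is no planned figure to reproduce.

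**Assumption.** Each value that can be missing is missing with probability q, taken as 2% to 5%, independently and completely at random.

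**Step 1: complete cases.** With m values that can be missing, the expected number retained is 25 × (1 − q)^m.

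| Cognitive model | q = 2% | q = 5% |
|---|---|---|
| Only the 6 post-treatment values can be missing | 25 × 0.886 = 22.1 | 25 × 0.735 = 18.4 |
| All 12 values can be missing | 25 × 0.785 = 19.6 | 25 × 0.540 = 13.5 |

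**Step 2: detectable effect.** This is the paired t-test at 80% power (noncentral t, n − 1 degrees of freedom). The effect is in SDs of the person-average change.

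| n | 25 | 22 | 20 | 18 | 14 |
|---|---|---|---|---|---|
| Detectable effect (SD) | 0.58 | 0.63 | 0.66 | 0.70 | 0.81 |

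All 25 complete therefore gives 0.58 SD. Post-treatment loss only gives 0.63-0.70, and loss across all 12 values gives 0.66-0.81.

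**Step 3: how much is avoidable.** A simulation of six correlated change scores (correlation 0.3 or 0.5, 25 people, all 12 values liable to be missing, 6,000 runs per setting) used an assumed effect of 0.6 SD, for which full-data power is 82%. The available-data estimate was a weighted mean that approximates a mixed model and takes the correlation as known.

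| q | Listwise power | Available-data power |
|---|---|---|
| 2% | about 71% | about 82% |
| 5% | about 52-53% | about 81% |

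Type I error was near 5% for both, as expected when data are missing completely at random. Under these assumptions nearly all of the loss is recoverable.

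**Step 4: circuit and quality-of-life models.** Independent loss over 10 or 8 values would leave 25 × 0.817 = 20.4 to 25 × 0.599 = 15.0 for the circuit model, and 25 × 0.851 = 21.3 to 25 × 0.663 = 16.6 for quality of life. That pattern is unlikely, because the circuit measures appear to come from the same scan and the four domains come from one questionnaire. If whole sessions are lost at 2-5% each, 25 × 0.98² = 24.0 to 25 × 0.95² = 22.6 remain. In that case there are few orphaned pairs for any available-data method to recover.

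**The case against.** Four objections carry weight.

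**Scope.** A reader might infer that one failed at-home test discards all of that person's other trial data. The SAP does not support this. It tests each modality separately, so on the ordinary reading a missing cognitive score costs that person's other cognitive scores and leaves imaging, quality of life, depression, life satisfaction and suicidality untouched. Wider loss would follow only if the list were the whole data set, which the SAP does not say.

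**Home testing.** The Protocol says that participants will "be sent instructions for completing cognitive testing at home", but only at the first screening visit. It does not say where post-treatment testing takes place, and it gives no failure rate. A failed home test cannot affect the circuit or quality-of-life models. Cognitive performance is also an entry criterion (Protocol 8.h), so some baseline failures would surface before enrolment. That protection is partial: the criterion joins Maze, Digit Span and Verbal Interference with and/or, and it does not list Switching of Attention. The post-treatment-only row of the working covers the case where baseline is complete.

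**Magnitude.** A reader might take the larger losses as a forecast for all three models. They rest on assumed rates and independent cells. Clustering shrinks them, most clearly for the circuit and quality-of-life models.

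**Bias.** It is tempting to say that listwise deletion is valid only under missing completely at random and that a mixed model cures this. Neither part holds as stated. The complete-case mean change is unbiased whenever missingness is unrelated to the change itself. If a test is missing because of its own unseen poor result, a mixed model that assumes missing at random does not generally repair that either.

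For the primary outcome, nothing in the SAP confines the paired t-tests to the GLM sample. All four objections stand as limits on the point. None removes the mechanism in the cognitive model.

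**Conclusion.** The point holds, chiefly for the secondary cognitive model. As written, one missing test at either session drops the participant from that model and wastes up to five intact pre/post pairs. At an assumed 2-5% missing per value, 25 participants become about 22 to 18 (post-treatment loss only) or about 20 to 14 (all 12 values, independent). The detectable paired effect moves from 0.58 SD to 0.63-0.70 or 0.66-0.81 SD. These figures depend on the assumed rates and on independence between values; clustering makes them smaller. For the circuit and quality-of-life models little is lost beyond whole-session dropout, and little is recoverable. The case for change rests on precision, with no claim that bias would be removed. It should be changed because a better method is available at small cost.

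**What to change.** In the SAP:

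1. Replace listwise deletion with an available-data analysis for the multi-measure models. For cognition, one suitable choice is a REML mixed model on the pre-to-post changes, with a separate mean for each test, a participant random intercept and, if it converges, test-specific residual variances. Use Kenward-Roger degrees of freedom and report the effect averaged equally over the six tests. Standardise each test to its baseline SD and sign it so that higher is better.
2. Run each planned paired t-test on all pairs complete for that measure.
3. Keep the listwise result as a sensitivity analysis, define its scope as the single model, and report the number analysed and the pattern of missing tests.

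**Cost.** This needs new SAP wording and a different model procedure, with no new data. Scaling and covariance structure must be fixed in advance, and the structure must be simple. An unstructured covariance over 12 cognitive values has 12 × 13 / 2 = 78 parameters, and over 10 circuit values 10 × 11 / 2 = 55, neither of which 25 people can support. The suggested change-score model needs 2 variance parameters, or 1 + 6 = 7 with test-specific variances. The analysis assumes missing at random and does not remove bias from tests missing because of their own unseen result.
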